5.1.2 INCLUDED EMS AGENCIES / REGIONS / HOSPITALS

- Local Fire Department First Responders using mechanical chest compression devices including:
 - Ann Arbor Fire Department First Responders
 - Ann Arbor Township Fire Department First Responders
 - Saline Area Fire Department
 - Scio Township Fire Department First Responders
 - Huron Valley Ambulance Paramedics
 - Michigan Medicine, University of Michigan

5.2 PARTICIPANT EXCLUSION CRITERIA

Exclusion criteria include:

- Sustained return of spontaneous circulation (ROSC)
- DNAR or DNI advanced directive
- Preexisting evidence of opting out of study
- Prisoner
- Pregnant (obvious or known)
- ECPR capable ED is not at the destination hospital as determined by EMS
- LAR/Family member aware of study and refuses study participation at the scene

5.3 STRATEGIES FOR RECRUITMENT AND RETENTION

There is no participant “recruitment” for this study as it is not possible to prospectively identify victims of out-of-hospital sudden cardiac arrest and obtain informed consent. Participants will be included in the study if they meet enrollment criteria at the time of their cardiac arrest. Based on historical data, we anticipate randomizing 30 refractory OHCA patients over 18 months. This clinical trial will be conducted under exception from informed consent (further details in Section 13).

Patients will be screened and assigned a randomization group at the time of dispatch. Study eligibility and randomization will be further determined with the aid of an algorithm or expected time to eligible hospital map where a 911 dispatch operator will input eligibility data points and receive one of 3 responses. This is pre-enrollment treatment group assignment. Despite assignment to one of these three groups, the patient will not be considered randomized until they have met the inclusion criteria (including the refractory nature of the cardiac arrest.)

1. Not eligible continue usual resuscitative care (stay in place until ROSC or resuscitation

meets termination criteria)

2. Eligible, randomized to usual care (operationally same as 1 for paramedics)
3. Eligible, randomized to early transport

After an initial rhythm assessment and shock delivery (if indicated), patients who do not have ROSC will be considered randomized. Based on the assignment given at the time the prehospital providers were dispatched, they will either continue usual care (stay in place until ROSC) if assigned to that group (control), or undergo expedited transport with mechanical CPR device in place (experimental group). Patients who do not meet inclusion criteria or have exclusion criteria will not be considered randomized or enrolled, since no experimental procedures will occur to them (standard procedure is for patients to be transported after ROSC). If ROSC is achieved during transport or in the emergency department (experimental group), they will be included in the primary analysis of the expedited transport group. All patients will be followed for clinical outcomes.

All Emergency Medical Services (EMS) personnel (engaged sites) will be trained by a member of the study team to the study protocol including randomization, eligibility, study procedures, exception from informed consent, and opting-out mechanisms. Training records will be maintained with the site coordinator.

In accordance with the FDA's Regulations, the investigator must attempt to notify all participants that they have been enrolled in a study. If the participant is unable to comprehend this due to loss of consciousness or dies, the investigator must attempt to notify their legally authorized representative.

Study participants who die in the field or the hospital emergency department, attempts will be made to notify their family/LAR, by using EMS and hospital records contact information. Initial contact will be made by a letter requiring a signature/receipt for receipt confirmation. With respect for the grieving process, a letter will be sent 2-4 weeks after the death of the patient. These records will also be reviewed and data abstracted, in addition to reviewing for any potential adverse events. Letters returned to sender or knowledge initial letter was not received, a telephone call will be made, up to 2 times for notification. This will be done by a trained research team member, experienced with discussing sensitive topics such as the death of a loved one. A communication tracking log will be kept.

Study Participants who survive to hospital admission or their LAR/family member will be approached to notify them of being in the research study and invited to continue study participation, as soon as feasible after hospital admission. The person obtaining consent will first discuss the study with the participant's physician or nurse to assess their condition and best timing for discussion with them or their LAR/family member. Once signed, a copy of this form is provided to the participant/LAR, in the medical record, and the original will be placed

in their research record.

We will conduct education and training of engaged agencies and hospitals to maximize recruitment. Screening logs will be reviewed regularly with engaged agencies.

5.4 PARTICIPANT WITHDRAWAL OR TERMINATION

5.4.1 REASONS FOR WITHDRAWAL OR TERMINATION

A study participant has the right to withdraw from the study at any time without consequence. Reasons for withdrawal may include not wanting to complete the 90-day follow-up visit, becoming tired with the follow-up surveys and requesting to stop, or deciding to no longer participate.

5.4.2 HANDLING OF PARTICIPANT WITHDRAWALS OR TERMINATION

FDA regulations require investigators to prepare and maintain adequate study files recording all observations and other pertinent information relative to the clinical trial and when a participant or LAR/family member withdraws further participation, the data already collected, remains with the study database.

If a study participant or LAR/family member declines further study participation, then no further data collection will occur. Since this is an observational study after randomization, the participant can safely withdraw and will not be at risk of injury.

In the case of participant withdrawal, data about their death is contained in public vital statistics records and will be queried. Access to public records is not subject to restriction under 21CFR or other FDA regulations.

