2.2 RATIONALE

Currently available evidence suggests that ECPR for OHCA should be initiated within 60 minutes of cardiac arrest onset to maximize the potential therapeutic benefit. Therefore, in addition to delivering patients to the ED within 30 minutes, it is essential that our system of care is able to initiate ECPR within ≤ 30 minutes of ED arrival. In a recently published study of ED-initiated ECPR, the median time from ECPR team arrival to initiation of ECPR was 20 minutes [IQR 15-30 minutes] [Stub 2014]. The goal is to achieve < 30 -minute arrival to cannulation for all patients meeting inclusion/exclusion criteria for ECPR therapy.

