6 STUDY INTERVENTION

This study is a comparison of two treatment strategies for refractory out-of-hospital cardiac arrest (OHCA): continued standard care in the field (control) versus expedited transport with ongoing mechanical CPR to a hospital capable of initiating extracorporeal cardiopulmonary resuscitation (ECPR) in the emergency department (experimental). ECPR is defined as percutaneous veno-arterial extracorporeal membrane oxygenation (ECMO) initiated during cardiac arrest. The duration of ECPR is typically 72 hours to allow the patient's heart function to recover prior to weaning. Many devices make up an ECMO circuit (cannulas, conduit, reservoir, pump, oxygenator, heat exchanger, monitors, sweep gas controller, bubble traps, blood filters, positive and negative pressure monitors and controls). The devices used for ECMO are FDA-approved for up to 6 hours for the indication of cardiopulmonary bypass. However, ECPR for the treatment of refractory cardiac arrest is not a FDA approved or cleared indication for ECMO devices, and thus is considered investigational in this study. Current American Heart Association Guidelines state that *"In settings where it can be rapidly implemented, ECPR may be considered for select cardiac arrest patients for whom the suspected etiology of the cardiac arrest is potentially reversible during a limited period of mechanical cardiorespiratory support (Class IIb, LOE C-LD)"*. ECPR is currently performed in the University of Michigan University Hospital ED for selected patients with refractory cardiac arrest as part of our standard practice. Examples of local guidelines for EMS and ED care are given as appendices B and C.

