7 STUDY PROCEDURES AND SCHEDULE

7.1 STUDY PROCEDURES/EVALUATIONS

7.1.1 Study specific procedures

Consent Process

Participants or their legally authorized representative (LAR) or family member will be approached within a reasonable timeframe and will be requested for consent to continue in the study. The availability and emotional state of LAR/family members will be taken into account, and anticipate a longer timeframe in these situations. The progress of obtaining written informed consent will be documented in the medical record. For participants who do not survive to hospital admission, a letter will be sent as notification.

Review of Medical Records

FDA's regulations require clinical investigators to prepare and maintain adequate and accurate case histories (21 CFR 312.62(b) and 812.140(a)). In general, the investigator should arrange to have access to all records that are generated and maintained from enrollment until discharge or death, unless the participant or their LAR/family member discontinues the participant's participation in the study. Medical records will be reviewed by a member of the research team up until this time and if the participant or LAR or family member discontinues participation, the data already collected will remain with the study.

Prehospital Medical Records

BLS and ACLS run reports will be reviewed on all study participants by the study team and study specific data abstracted. Run reports become part of the medical record when patients are brought to the emergency department and for cardiac arrests pronounced dead in the field, will be sent to the study team securely (i.e. by fax).

The following scales will be performed by a member of the research team at hospital discharge and Day 90, in participants who survive.

Modified Rankin Scale (mRS)

The mRS is commonly used for measuring the degree of disability or dependence in the daily activities of people who have suffered a neurological disability. mRS score is widely used in stroke research.

Cerebral Performance Categories Scale (CPC)

CPC score is widely used in cardiac arrest research to assess neurologic outcome.

NIH Toolbox

The NIH toolbox includes several cognitive, motor, and psychological tests. It can be administered via an iPad.

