7.3.5 EARLY TERMINATION VISIT

Prehospital patients in cardiac arrest will not have the ability to notify prehospital providers of their choice to participate or not. If a LAR/family member is aware of the study and objects to their participation, prehospital providers will not enroll the patient.

If the participant survives to hospital admission, a member of the study team will attempt to contact the participant or LAR/family member to notify them of study participation and obtain informed consent for continued participation in the study. The participant or LAR or family member has the right to decline study participation at any time before or after informed consent is obtained. A participant, however may not withdraw use of the data already collected. At the point of termination, the medical record will no longer be reviewed. However, data about a participant's death is contained in public vital statistics records. Access to public records is not subject to restriction under 21 CFR 50.24 or other FDA regulations.

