Participants enrolled in EROCA with EFIC, or their LAR/family member(s), will be informed of study enrollment in the clinical investigation at the earliest possible opportunity. Participants admitted to the hospital will be approached in person. A study team member will speak with the senior clinician to determine the stability of the participant and the appropriate time for speaking with the participant, or if not alert and capable of making informed decisions, a LAR or family member. The study team member will approach the participant(or LAR/family) to notify them about the participant's enrollment under EFIC, provide information about the study, including continued enrollment.

Participant's rights, the responsibilities of the investigators, and answer any questions about the study. At that time, the patient or the LAR will be asked to provide consent for continued participation in the study. A written informed consent document will be used to document the decision to either continue in the study or to not participate any further. A copy of this form will be provided to the participant and another copy will be placed in the research record.

Participants who do not wish to continue to participate will be excluded from all further aspects of the study except for the collection of data required by the FDA and permitted by the IRB to determine safety and efficacy. If informed consent is provided by a LAR or family member, we will approach the subject at the earliest possible opportunity to seek prospective, written informed consent for continuing participation in the study, should they become capable of doing so.

It is anticipated that the notification of participants of LAR/family member(s) will commonly take place in the hospital within 12-24 hours of their cardiac arrest. If the participant remains unable to participate in this process and family members or another legally authorized representative are not present, continued attempts will be made to contact an LAR. Attempts to notify the participant or an LAR will be repeated three times after the patient has been initially enrolled. All notification attempts will be recorded on the subject's case report form. Reports of these logs will be included in annual reports to the IRB.

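### Sections 5.4.2, 7.3.5 and 7.1.1 end medical-record review when a participant or family declines, while Appendix A keeps a conditional safety exception; non-fatal complications after an early refusal can go unrecorded

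*Combined protocol and SAP*

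**What the plan says.** Three sections in the body of the protocol describe what happens when a participant, legally authorized representative or family member declines to go on:

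- Section 5.4.2: if that person "declines further study participation, then no further data collection will occur". Data already in the database stay, and death is looked up in public vital records.
- Section 7.3.5: "At the point of termination, the medical record will no longer be reviewed". The same section says that the participant or family "has the right to decline study participation at any time before or after informed consent is obtained".
- Section 7.1.1: the investigator should have access to records up to discharge or death, "unless the participant or their LAR/family member discontinues the participant's participation in the study".

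Appendix A (EFIC plan, part on contacting representatives and family) has people who do not want to go on take no more part in the trial, with one reservation: "except for the collection of data required by the FDA and permitted by the IRB to determine safety and efficacy". It also says that notification "will commonly take place in the hospital within 12-24 hours of their cardiac arrest". At that meeting the patient or representative is asked to consent to continued participation.

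On treatment duration, section 6 says: "The duration of ECPR is typically 72 hours".

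**The concern.** The three body sections contain no safety exception and the appendix contains one. A coordinator whose patient's family has just declined cannot tell from the documents whether the chart must be closed or whether some safety abstraction may continue.

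Timing makes this more than a wording problem. The first request to continue is expected while a cannulated patient would typically still be on ECPR. Section 3 makes it an objective to estimate how often adverse events associated with the interventions occur. Section 6 calls ECPR investigational for this indication. Section 7.3.2 makes existing medical records the only data source until discharge. If record review stops, there is no second route to a non-fatal complication.

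The safety sections do not settle the matter. Section 8.3 wants adverse events followed until they resolve. Section 8.4.1 ends follow-up at the end of study for that subject, and ends the SAE window at 90 days or the last day of participation. A refusal therefore closes the window as well.

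**Working it through.** The plan states no figure on this point, so the check is a comparison of texts and a short piece of time arithmetic.

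**1. What survives a refusal under each rule**

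| Item | 5.4.2, 7.3.5, 7.1.1 | Appendix A |
|---|---|---|
| Data collected before refusal | Kept | Not at issue |
| Death after refusal | From public records (5.4.2, 7.3.5) | Within the exception if required and permitted |
| Non-fatal event first arising after refusal | Not collected | Within the exception if required and permitted |

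The two rules part company on the last row.

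**2. How much of an ECPR run lies after an early refusal**

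Inputs:
- Time of notification: 12 to 24 h after arrest (Appendix A).
- ECPR duration: 72 h, typical (section 6).
- ECPR start: section 2.2 says that "ECPR for OHCA should be initiated within 60 minutes of cardiac arrest onset", so take 0 to 1 h after arrest.

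Formula: hours outside review = (ECPR start + 72) − time of refusal; share = hours ÷ 72.

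- Refusal at 24 h: 0 + 72 − 24 = 48 h (48/72 = 67%) to 1 + 72 − 24 = 49 h (49/72 = 68%).
- Refusal at 12 h: 0 + 72 − 12 = 60 h (60/72 = 83%) to 1 + 72 − 12 = 61 h (61/72 = 85%).

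About 48-60 h of a typical run would fall outside record review, followed by the rest of the hospital stay. This supposes refusal at the first notification and a run of typical length.

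**3. Which events are exposed**

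Section 4.2.2 lists, among others, hemorrhage needing transfusion, vessel damage, thromboembolism, stroke, renal failure and infection. Section 4.2.3 adds liver and splenic injury. Non-fatal events of these kinds that first arise after refusal are the ones lost. Events before refusal, and deaths at any time, are not.

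**4. What one event weighs**

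At most 30 patients are randomized, 4:1 in favour of early transport (section 10.6.1): 30 × 4/5 = 24. With all 24 in the denominator, one unrecorded event moves a rate by 1/24 = 4.2 percentage points. Among cannulated patients alone the denominator is smaller or equal, so the shift is at least as large.

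**5. What cannot be computed**

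The documents give no refusal rate, no expected number surviving to admission after early transport, and no rate of post-refusal complications. The number of missed events cannot be derived from them.

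**6. Primary endpoints**

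Both co-primary endpoints are time intervals that end with ED arrival or the start of ECPR on day 0. They are complete hours before any refusal at 12-24 h.

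**The case against.** The strongest reply is that this is an ambiguity and not a contradiction. The appendix exception covers only what the FDA requires and the IRB permits. The body can be read as stating what that amounts to: keep what was collected and take death from public records. Section 7.1.1 cites FDA record-keeping rules and then limits access to the time before discontinuation. On that reading the rules agree. This stands in part: a reader might infer that Appendix A promises full safety follow-up after refusal, and it does not. But the body never mentions the exception or says that it is empty, so a site still lacks an answer.

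The timing is also an early case. Section 7.1.1 anticipates longer for some families, section 5.3 lets the treating clinician advise on when to approach, and Appendix A allows repeated attempts. This stands: 48-60 h describes a refusal at the first common time of contact. A later refusal loses less of the ECPR run.

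Stopping chart review after refusal, when nobody consented to enrollment, is a defensible protection of participants. This stands too, and it is why continued review must depend on the IRB. The continuing-participation form is not in the public documents, so it may already separate visits from record review.

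Three further inferences are tempting and unsupported:

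- That withdrawn patients will be counted as event-free. No section says so. Section 8.6 gives the DSMB a listing by individual, and section 10.4.5 summarizes reasons for withdrawal. What is missing is a rule for showing when observation ended.
- That families refuse more often after a bad course, so that event rates are biased downward. Nothing in the documents bears on this.
- That section 5.4.1 expects most withdrawals to concern the day-90 visit and surveys. It gives these only as possible reasons, alongside simply deciding to stop.

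**Conclusion.** The concern holds in a limited form. The body sections and Appendix A give different rules for safety data after refusal and must be reconciled. If the body is followed as written, a refusal at the first common time of contact leaves roughly two thirds to five sixths of a typical ECPR run, and the remaining stay, without any record of non-fatal section 4.2.2 and 4.2.3 events.

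This rests on the documents' own 12-24 h and 72 h and on refusal at first approach. How many patients this would affect is unknown. It may be none, but in a trial of at most 30 patients with descriptive safety reporting, one or two truncated records would matter. The feasibility conclusions on the co-primary endpoints are untouched.

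**What to change.** 1. State in sections 5.4.2, 7.3.5 and 7.1.1 that the Appendix A exception applies.
2. As the IRB permits, offer two separate choices on the continuing-participation form: declining interviews, testing and the day-90 visit; and declining further review of the hospital record for safety. Unless the second is declined, chart review for the section 4.2.2 and 4.2.3 events and SAEs continues to discharge. Families keep the right to refuse both.
3. In the safety tables and listings, give the date on which observation ended for anyone whose record review stopped, and count that person as incompletely observed, not as event-free. This is worth doing whichever rule the IRB adopts.

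The cost is wording in three sections, a slightly longer form and an IRB amendment. Chart abstraction through discharge is already planned, so no new data source is needed. Whether review may continue after a refusal is for the IRB to decide.

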5.5 PREMATURE TERMINATION OR SUSPENSION OF STUDY

This study may be temporarily suspended or prematurely terminated if there is sufficient reasonable cause. Written notification, documenting the reason for study suspension or termination, will be provided by the suspending or terminating party to the investigator, funding agency, the IND/IDE sponsor and regulatory authorities. If the study is prematurely terminated or suspended, the PI will promptly inform the IRB and will provide the reason(s) for the termination or suspension.

Circumstances that may warrant termination or suspension include, but are not limited to:

- Determination of unexpected, significant, or unacceptable risk to participants
- Demonstration of efficacy that would warrant stopping
- Insufficient compliance to protocol requirements

- Data that are not sufficiently complete and/or evaluable
- Determination of futility

Study may resume once concerns about safety, protocol compliance, data quality is addressed and satisfy the sponsor, IRB and/or FDA.

